1. Protocol Title

Spinal Cord Injury Exercise and Nutrition Conceptual Engagement (SCIENCE)

2. Objectives

The specific objectives for the current proposal are to assess the impact of home-based functional electrical stimulation leg cycle ergometry plus diet (HBFESLCE + Diet) versus Diet Alone on (Primary Variables) body composition (%BF, FM and FFM), insulin sensitivity (SI), glucose effectiveness (SG), and BMR, as well as (Secondary Variables) lower extremity bone mineral density, lipid profiles, and hsCRP in adults with motor complete SCI between C4-T4. Specific objectives to be addressed in the current proposal are:

1. To determine the impact of HBFESLCE + Diet on body composition, insulin sensitivity, glucose effectiveness and BMR in adults with motor complete tetraplegia or high paraplegia above T4. Additionally, lower extremity bone mineral density & content, lipid profiles, and hsCRP will be compared before and after intervention.
2. To determine the impact of HB Diet Alone on body composition, insulin sensitivity and glucose effectiveness in adults with motor complete tetraplegia or high paraplegia. Additionally, lower extremity bone mineral density, lipid profiles, and hsCRP will be compared before and after intervention.
3. To compare the efficacy of HBFESLCE + Diet with that of HB Diet Alone relative to the parameters listed above.
4. To create a robust dataset of variables that are associated with visceral adipose tissue (VAT) to predict determinates of epicardial VAT (EAT) and abdominal VAT (AVAT) in subjects with chronic motor complete C4-T4 SCI.
5. To compare the change in epicardial adipose tissue, abdominal visceral adipose tissue, intramuscular fat, and subcutaneous adipose tissue before and after home-based FES-LCE plus diet vs. diet alone in adults with chronic motor complete C4-T4 SCI.
6. To compare changes in circulating proinflammatory adipokines before and after FES-LCE plus diet vs. diet alone in adults with chronic motor complete C4-T4 SCI.

3. Background

There are an estimated 1.5 million persons in the United States with SCI, Men 3x > Women, with ~50% having tetraplegia and recent literature would imply that more than 60% are overweight or obese by BMI standards, more than 50% are glucose intolerant,

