5. Number of Subjects

Forty (40) subjects will participate in the study; however, it may be necessary to screen up to 60 subjects to allow for those who do not meet inclusion/exclusion criteria.

Study Timelines

It is anticipated that subjects will be enrolled in the study for 21 weeks.

It is anticipated that enrollment of subjects will occur between August 15, 2020 and December 31, 2024.

6. Study Endpoints

Primary Study Endpoints:

1. Body composition (%BF, FM and FFM)
2. Insulin sensitivity
3. Glucose effectiveness

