4. BMR
5. Thickness of epicardial adipose tissue as measured by echocardiography
6. Volumes of subcutaneous adipose tissue (SAT), visceral adipose tissue (VAT), intramuscular fat, (IMF) as measured by CT.

Secondary Study Endpoints

1. Lipid profiles
2. Lower extremity bone mineral density
3. hsCRP in adults

4. Proinflammatory adipokines: tumor necrosis factor- α , interleukin-6, monocyte chemoattractant protein-1, plasminogen-activator inhibitor-1, vascular cell adhesion molecule-1 and intercellular adhesion molecule-1
5. Anti-inflammatory adipokines: Adiponectin and Interleukin-10

7. Procedures Involved

Overview:

Primary outcome measures will include body composition by iDXA, CT, Echocardiography, insulin sensitivity, glucose effectiveness and BMR, while secondary outcomes will include lower extremity BMC and density, lipid profiles, hsCRP, fasting insulin, TNF α , IL-6, PAI-1, ICAM-1, VCAM-1 MCP-1, adiponectin and IL-10, Non-esterified free fatty acids determined before and after the 16-week interventions. Subjects will be randomly assigned (50% chance) to either HBFES LCE + Diet on an RT300 ergometer or Home-based (HB) Diet Alone intervention as determined by a random number generator.

Study Procedures include:

- **History and Physical Examination:** Each subject will undergo a complete history and physical examination by a physiatrist board certified in SCI medicine. This will include general demographics, past medical history, medications, family and social history, race and ethnicity. Subjects will undergo an AIS exam which is a system of tests used to define and describe the extent and severity of a patient's spinal cord injury. 28 key sensory points will be tested on each side of the body for light touch and pinprick sensations. There will also be a strength assessment of ten muscles on each side of the body. The subject will be graded based on their sensations and strength assessment. Subjects who have had a neurological physical exam with ASIA completed in the last year by a licensed physiatrist board certified, will not need a repeat exam. Women of childbearing potential will have a pregnancy test obtained.
- **ECG:** A resting 12-lead ECG will be performed on each subject to rule out any coronary artery disease.

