- **Surface Neurostimulation:** The physical exam will conclude with a surface neurostimulator trial to determine muscle response to electrical stimulation at bilateral gluteus maximus, hamstrings, vastus lateralis, and vastus medialis. If there is no muscle response, the patient may not be included in the study.
- **Dobutamine Echocardiogram/Epicardial Adipose Tissue**

- **Screening Labs:** A full electrolyte panel (fasting sodium, potassium, chloride, bicarbonate), BUN, creatine, glucose and HgbA1c will be drawn at the Clinical Translational Research Site, 7th floor during the IVGTT.
- **Blood labs**
 - **Blood Lipids, hsCRP and inflammatory panels:** Each subject will have lipid profiles (HDL-c, LDL-c, total cholesterol, and triglycerides). hsCRP, insulin, non-esterified free fatty acids, IL-6, TNF α , MCP-1, PAI-1, ICAM-1, VCAM-1, Adiponectin, IL-10 assessed before and after the 16-week intervention. Lipids and hsCRP will be determined by standard analyses procedures employed by the CRC. Secondary variables of particular note include HDL-c, total cholesterol:HDL-c ratio and hsCRP.
 - **Genetic Testing:** A separate sample will be collected and stored for future analysis to assess genetics in relation to body composition and metabolism after spinal cord injury.
- A total of approximately 26 ml of blood (approximately 5 teaspoons) will be collected for all the aforementioned tests.
- **Body Composition:** Dual Energy X-Ray Absorptiometry (DXA): Total body and regional (lumbarspine, proximal femur, and forearm) dual-energy x-ray absorptiometry (DXA) scans will be performed using a Lunar iDXA bone densitometer at the Lynn Rehabilitation Center Physical Medicine and Rehabilitation (Lynn PM&R) Research Lab. DXA scans will be completed at screening, baseline, and at the midpoint and end of the study intervention to assess for changes in body composition. All scans will be performed and analyzed by a trained, certified DXA operator. A single trained investigator will analyze all scans. The DXA total bone mineral content measurements will be used to correct for the mineral fraction in the criterion body composition model (4-compartment model) [39]. Anthropometric measures (skinfolds, girths and circumferences) will be obtained for pilot data using a CRC adjunct proposal. Primary variables will include %BF, Absolute Fat Mass (FM), and Absolute FFM determined by DXA.
- **Weight:** Subjects will be weighed at each visit to the Lynn PM&R Research Lab.

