n=10 per group	99%	98%	95%	79%

n=15 per group	100%	100%	99%	90%
n=20 per group	100%	100%	100%	97%
Mean Diff(T2-T1) Group 1=0.0, Group 2=1.6				
$\alpha = 0.05$	Var(Time1)=Var(Time 2)=3.00		Var(Time1)=Var(Time 2)=6.00	
Sample Size	Empirical Power $\rho=0.70$	Empirical Power $\rho=0.50$	Empirical Power $\rho=0.70$	Empirical Power $\rho=0.50$
n=10 per group	72%	49%	45%	31%
n=15 per group	88%	68%	57%	40%

All primary and secondary outcomes will be visually assessed (boxplots, histograms, etc.) for normality and/or continuous data will be examined with a Shapiro-Wilk test. We will use a 2-way (group x time) mixed-model analysis of variance (ANOVA) to assess group interaction. Where significant interaction effects are observed, paired and independent t-tests will be used to determine significant differences within and between groups. Alpha will be set at < 5%.

11) Provisions to Monitor the Data to Ensure the Safety of Subjects

Please refer to the attached document DSMB 0719

12) Withdrawal of Subjects

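### Six or ten primary variables depending on the section, each tested at two-sided 5% with no multiplicity rule or success criterion; the body composition method is also stated two ways

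*Combined protocol and SAP*

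**What the plan says.** **Primary labels.** Section 2 (Objectives) marks six variables: "Primary Variables) body composition (%BF, FM and FFM), insulin sensitivity (SI), glucose effectiveness (SG), and BMR". The primary list in section 6 (Study Endpoints) opens with "Body composition (%BF, FM and FFM", continues with insulin sensitivity, glucose effectiveness and BMR, then adds "Thickness of epicardial adipose tissue as measured by echocardiography" and "Volumes of subcutaneous adipose tissue (SAT), visceral adipose tissue (VAT), intramuscular fat, (IMF) as measured by CT". That makes ten. The section 7 Overview follows the same domains: "Primary outcome measures will include body composition by iDXA, CT, Echocardiography, insulin sensitivity, glucose effectiveness and BMR". The Stress Test & Energy Expenditure item in section 7 also calls exercise energy expenditure primary. It is measured during FES cycling sessions, which only the HBFES LCE + Diet arm has.

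**Statistical section.** Section 10, Statistical methods, names per cent and absolute fat, per cent and absolute FFM, SI, SG and BMR. It names no CT or echocardiography variable. It puts every test at two-sided 0.05 and closes with "Alpha will be set at < 5" (per cent). Sample size determination singles out %BF and SI as the variables that drove the sizing.

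**Body composition method.** The Body Composition item in section 7 says "Primary variables will include %BF, Absolute Fat Mass (FM), and Absolute FFM determined by DXA", and Sample size determination also sizes %BF by DXA. Statistical methods attributes the same variables to 4-compartment modelling.

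**The concern.** A reader cannot tell from the plan which results decide whether the trial succeeded. The sections disagree on what is primary. Nothing orders the tests, divides the alpha or says how many significant results are needed. One p<0.05 among six or ten variables could therefore be presented as a primary finding at a nominal 5%, when the chance of such a finding with no true effect is well above 5%. The stated power (80% or more for %BF at 20 per group) is also power for a single unadjusted test, so it does not describe a trial with several primary variables once error is controlled. On method, two analysts following different sections would name different sources for the same primary variable.

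**Working it through.** **1. Reproduce the plan's power for %BF.** Inputs from Sample size determination: change 31.8 − 28.5 = 3.30 points in the exercise arm and 0.06 in Diet alone, so the difference is 3.24; variance 6.25 or 12.5; pre–post correlation ρ 0.7 or 0.5; 20 per group. SD of change = √(2·Var·(1−ρ)). In the least favourable case this is √(2·12.5·0.5) = 3.54, with standard error 3.54·√(2/20) = 1.12 and noncentrality 3.24/1.12 = 2.90 on 38 df. Two-sided 5% power is 80.6%, against 80% in the plan. All four cells at 20 per group agree within 2 points (table in step 4).

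**2. Count the tests.** Section 2 gives six and section 6 gives ten. The Statistical methods list has seven entries, but if FFM is body mass minus fat mass, per cent FFM is 100 − %BF and its change gives the same p-value. Six distinct tests remain. Exercise energy expenditure has no between-group test and is not counted.

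**3. Chance of at least one p<0.05 with no true effect.** Independent tests: 1 − 0.95^k, which is 26.5% for k=6 and 40.1% for k=10. For correlated tests, two-sample t-tests on change scores were simulated at 20 per arm (200,000 runs). The correlations are assumptions.

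| Common correlation | Six | Ten |
|---|---|---|
| 0.3 | 24.3% | 35.4% |
| 0.5 | 20.9% | 29.1% |
| 0.7 | 16.8% | 21.9% |
| 0.9 | 11.1% | 13.1% |

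A normal-theory integral gives 24.1% and 10.8% (six) and 35.1% and 12.8% (ten) at the two ends. One common correlation is crude, so three block structures were also tried. The within-block correlations (body composition / SI, SG, BMR / four fat depots) and the between-block correlation were 0.8/0.2/0.6 and 0.2; 0.9/0.3/0.7 and 0.3; 0.9/0.2/0.5 and 0.1. Results: six 22.1%, 20.5%, 21.2%; ten 32.8%, 29.5%, 33.9%. For %BF and SI alone the unadjusted figure is 7.1–9.8%; with Holm it is 3.6–4.9%.

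**4. Power at the first Holm step (0.05/2 = 2.5%), 20 per arm.**

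| Endpoint, variance, ρ | Plan, 5% | Computed, 5% | Computed, 2.5% |
|---|---|---|---|
| %BF, 6.25, 0.7 | 100% | 99.9% | 99.8% |
| %BF, 6.25, 0.5 | 97% | 97.9% | 95.7% |
| %BF, 12.5, 0.7 | 95% | 95.4% | 91.5% |
| %BF, 12.5, 0.5 | 80% | 80.6% | 71.2% |
| SI difference 1.6, 3, 0.7 | – | 95.7% | 92.0% |
| SI difference 1.6, 3, 0.5 | – | 81.2% | 72.0% |
| SI difference 1.6, 6, 0.7 | – | 73.9% | 63.2% |
| SI difference 1.6, 6, 0.5 | – | 52.1% | 40.4% |

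The SI table as available has no 20-per-group row for a difference of 1.6. At 15 per group the same method gives 88.3, 68.5, 60.6 and 40.8%, against 88, 68, 57 and 40% in the plan. At 17 per arm (15% dropout) the least favourable %BF case goes from 73.6% to 62.7%.

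**5. Scale of the SI inputs.** The text calls 3 and 6 standard deviations; the tables use them as variances. If they are SDs of each measurement, power for 1.6 at 20 per arm is 37.6–56.4% (SD 3) or 13.0–18.6% (SD 6) at 5%, and 27.1–44.6% or 7.8–11.8% at 2.5%.

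**6. DXA or 4-compartment.** The Background describes the 4-compartment model as including water, and section 3.2 treats DXA as a proxy for it. Section 7 adds "The DXA total bone mineral content measurements will be used to correct for the mineral fraction in the criterion body composition model (4-compartment model". That supplies the mineral term only. No procedure in the available text (a block near 17) Setting was not available) measures body water or body density.

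**The case against.** Several points on the other side have force.

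- **The lists may not be rivals.** Section 6 and the section 7 Overview agree on domains, Objective 5 in section 2 covers the fat depots, and the closing paragraph of Statistical methods extends to all primary and secondary outcomes. The ten-variable list could be taken as the definition and the others as incomplete restatements. This stands as a softer description, but it leaves the larger family and still no rule.
- **A reader might infer a third, seven-variable primary family with its own error rate of about 12–27%.** The documents do not support that. Statistical methods attaches the primary label only to SI, SG and BMR, and per cent FFM repeats the %BF test.
- **A reader might take 35% as this trial's error rate.** It is not. It needs ten variables, an assumed correlation of 0.3 and a rule that any one result suffices. The plan states neither the correlation nor that rule, though it does not exclude the rule.
- **%BF and SI might already be the confirmatory pair.** The remark explains sizing and does not restrict the claim. Even so, the unadjusted rate would be 7–10%.
- **The interaction test comes before the follow-up t-tests.** It works within one outcome and gives no control across outcomes.
- **A reader might infer that %BF cannot be obtained as planned.** DXA gives it; the 4-compartment wording is a conflict of text, with no numerical effect shown.
- **Holm on two endpoints is one choice.** A single primary or a fixed sequence would also solve the problem. Holm is proposed because the sponsor sized both endpoints.

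**Conclusion.** The concern holds. The primary designation is inconsistent, with six variables in section 2, ten in section 6 and a stray label in section 7. Every test is at two-sided 5%, with no multiplicity rule or success criterion. The false-positive chance is about 11–24% for six variables and 13–35% for ten at assumed equal correlations of 0.9 to 0.3, or about 20–22% and 30–34% under the assumed block structures. These figures assume no true effect, one test per variable and success on any single p<0.05. Even at correlation 0.9 both are more than twice the nominal level, and independence would put them higher than the quoted ranges. The naming of 4-compartment modelling is a wording conflict with DXA that needs correcting.

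**What to change.** 1. **One list.** Use the same primary list in section 2, section 6, the section 7 Overview and items (Body Composition, IVGTT, Stress Test & Energy Expenditure) and Statistical methods: %BF by DXA and SI. Make the other listed variables secondary, with the 95% confidence intervals already planned and no confirmatory claim. Report exercise energy expenditure descriptively, exercise arm only.
2. **One rule.** Amend both the opening statement that puts all tests at two-sided 0.05 and the closing "Alpha will be set at < 5" sentence. Suggested text: *%BF and SI are tested with Holm at overall two-sided 5%; all other tests are at nominal 5%.* Take each Holm p-value from the planned regression of the pre-to-post change on Group. Each endpoint then has one test, and the midpoint DXA scan does not enter it through the group-by-time ANOVA.
3. **Power.** First reconcile whether 3 and 6 are standard deviations or variances for SI. Then restate power at the 2.5% step. For %BF it is 99.8%, 96%, 92% and 71%, so the claim of more than 80% in every scenario must go. For an SI difference of 1.6, on the variance reading, it is 92%, 72%, 63% and 40%.
4. **Method.** Replace 4-compartment modelling with DXA in Statistical methods and align the 4-compartment sentence under Body Composition.

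**Cost.** No new data are needed. Eight of the ten listed variables lose the primary label, and some power is lost. The 2.5% figures are the worst case, because an endpoint is tested at 5% once the other is significant. Keeping all ten primary under Holm would cost more: the first step is 0.5%, and the least favourable %BF scenario falls to 48%. Timing also matters. Study Timelines anticipates enrolment to the end of 2024, and the version label, if 071825 is a date, points to July 2025, so follow-up may be complete. The actual status is unknown. The change must be a dated amendment made without knowledge of results by group.

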12.1 Criteria for removal from study

Subjects will be removed from the study for the following reasons:

- Withdrawn Consent
- Non-compliance with study requirements
- Recurrent Autonomic Dysreflexia

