lengthening bouts until at least continuous 40-minute sessions are tolerated. However, subjects will have the flexibility to advance through the accommodation period at their own pace, as tolerated. Exercise intensity during the remaining 12-week intervention will be set at 70% maximal heart rate (HRmax), as determined by the initial dobutamine stress test, or as close to that as tolerated / capable by the subject based on stimulation intensity and resistance (see below). Exercise training will consist of three to five, 40-67-minute sessions (200 minutes at target intensity) each week for a total of 16 weeks; 10-minute warm-up and cool-down sessions will accompany each exercise session. An intent-to-treat protocol will be employed, and thus all subjects randomized will be used in the final data analyses. FES leg cycle ergometry (LCE) training will be induced on the RT300 FES-LCE ergometer (Restorative Therapeutics, Inc., Baltimore, MD) through wires connected to silastic surface electrodes over bilateral quadriceps, hamstring and gluteal muscles. Electrodes will be placed on the skin of the following corresponding skeletal muscle groups. Quadriceps: One electrode will be placed on the skin approximately 3 finger widths above the superior aspect of the patella, and the other 4-5 finger widths from the inguinal crease. The Q-angle should be kept in mind when centering the electrodes over the quadriceps. Hamstrings: One electrode will be placed 2-3 finger widths above the popliteal fossa and the other electrode approximately 1 hand width apart but no further than 3-4 finger widths from the gluteal fold. Gluteus Maximus: Two electrodes will be placed parallel and on the bulk of the muscle belly with at least 2 finger widths between electrodes. The medial electrode will be placed approximately 2-3 finger widths from and parallel to the gluteal cleft and the lateral electrode approximately 2-3 finger widths posterior to the greater trochanter. The above are guidelines and due to anatomical differences among subjects, slight modifications may be required at the discretion of the Physical Therapist in order to achieve optimal tetanic contraction. Subjects will be provided with a pictorial instructional guide on proper electrode placement. (FES Protocol for Patient and Families Appendix 6).

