12.2 Follow-up for withdrawn subjects

Subjects withdrawn from the study prior to the 16-week assessment will be asked to return to the lab for an End of Study visit. These subjects will be asked to complete all baseline assessments. Subjects may refuse any or all of the End of Study procedures. At a minimum, investigators will require subjects to return the exercise equipment.

Subjects who are withdrawn early will not be replaced; we anticipate an Intent-to-Treat analysis of all subjects who complete screening and are randomized.

Subjects removed from the study for adverse events or safety concerns will be followed for resolution of the event. No additional follow up of withdrawn subjects will be performed.

13) Risks to Subjects

- Venous catheter Insertion may result in localized swelling, soreness, bruising, chance of infection, bleeding, pain, lightheadedness or possible fainting.
- Insulin Sensitivity Tests may result in hypoglycemia (low blood sugar) with occasional dizziness, sweating, and nausea. Seizures, coma or death may occur, but are highly unlikely during medical monitoring.
- Dobutamine echocardiogram may cause anxiety or dizziness.
- Anthropometrics may cause discomfort or bruising.
- Basal metabolic rate determination may cause anxiety or shortness of breath.
- Functional electrical stimulation may result in a fracture of the lower extremity and cause redness and skin lesions affecting the areas of electrode placement. The severity of the lesions may range from mild skin irritation to lesions that require treatment. Adherence to the *recommended* protocol for treatment and prevention of skin lesions will be provided to subjects. This protocol is as follows:
 - During the FES session in the first few weeks we will gradually increase amplitude while keeping a narrow pulse width. Pulse width will be gradually increased thereafter.
 - After each FESLCE session participants will be instructed to 1) wash the areas with soap and warm water, 2) thoroughly dry and apply over-the-counter Neosporin or any other over-the-counter triple antibiotic ointment or cream to the affected areas, and 3) cessation of fabrifoam wraps. After each session, the research team will request photos of the skin where the electrodes are placed for a post-session skin assessment.
 - Prior to the start of the FES sessions and throughout the protocol we recommend that all participants clip their hair.
 - When lesions begin to appear, stimulation will be decreased.

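### Removing non-compliant subjects from the study, with only a refusable and undated exit visit, undermines the planned intent-to-treat analysis

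*Combined protocol and SAP*

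**What the plan says.** Section 12.1 is worded as mandatory: "Subjects will be removed from the study for the following reasons". One of the three reasons is "Non-compliance with study requirements". The rule names no arm, defines no threshold, and concerns the study as a whole, not the intervention alone.

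Section 12.2 sets out what follows:

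- "Subjects withdrawn from the study prior to the 16-week assessment will be asked to return to the lab for an End of Study visit". No date is attached to this visit.
- "Subjects may refuse any or all of the End of Study procedures".
- "No additional follow up of withdrawn subjects will be performed". The only exception is following an adverse event or safety concern to resolution.
- Withdrawn subjects are not replaced, and "we anticipate an Intent-to-Treat analysis of all subjects who complete screening and are randomized".

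Section 7 (Procedures Involved, Exercise Training Intervention) makes the same promise: "An intent-to-treat protocol will be employed, and thus all subjects randomized will be used in the final data analyses".

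Section 10 (Statistical methods) plans a linear regression on post-minus-pre change scores and a group-by-time mixed-model ANOVA. It gives no rule for a missing final value or for one taken early.

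**The concern.** Whether a subject complies is decided after randomisation and can depend on the assigned treatment. If non-compliance ends study participation, the final outcomes available for analysis are partly selected by how treatment went. A subject without a post value has no change score, so the regression omits that subject. A mixed model could retain the baseline value, but that carries no information on change, and the result would rest on an unstated missing-at-random assumption.

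At stake is the primary between-arm comparison. In a trial of home-based treatment, the outcomes of people who do not keep up are part of the effect being estimated. Losing them moves the comparison toward adherent subjects, while the report would still be labelled intent-to-treat.

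**Working it through.** **Inputs** (Section 10, Sample size determination, unless noted)

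- Percent body fat (%BF), exercise plus diet: 31.8 to 28.5, a fall of 3.3 points.
- %BF, diet alone: a fall of 0.06. Planned difference: 3.3 − 0.06 = 3.24.
- 20 subjects per arm; two-sided alpha 0.05; variance 6.25 or 12.5; pre-post correlation 0.70 or 0.50.
- Dropout 15%: 0.15 × 20 = 3 per arm if equal. This covers dropout for any reason.
- Assumptions not in the documents: 3 exercise subjects are removed for non-compliance, and they would show no exercise benefit at week 16.

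**Step 1: reproduce the plan's power.** SD of change = √(2 × variance × (1 − correlation)), with a two-sample t-test on change scores, 20 per arm and a difference of 3.24.

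| Variance, correlation | SD of change | Power recomputed | Power stated |
|---|---|---|---|
| 6.25, 0.70 | 1.94 | 99.9% | 100% |
| 6.25, 0.50 | 2.50 | 97.9% | 97% |
| 12.5, 0.70 | 2.74 | 95.4% | 95% |
| 12.5, 0.50 | 3.54 | 80.6% | 80% |

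The stated figures are reproduced, so 3.24 is the right planning difference to work from.

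**Step 2: difference if everyone is followed to week 16.** 3.3 × 17/20 − 0.06 = 2.805 − 0.06 = 2.745.

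**Step 3: what the plan as written would estimate.**

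- No exit data from the three: the 17 remaining give 3.3 − 0.06 = 3.24. Ratio 3.24/2.745 = 1.18, an overstatement of 18%.
- Exit data obtained, no change at exit: 2.745, so 0%.
- Exit data at an early visit showing 25% of the effect, gone by week 16: 3.3 × (17 + 0.75)/20 − 0.06 = 2.87, or +5%. With 50%: 3.3 × (17 + 1.5)/20 − 0.06 = 2.99, or +9%.

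**Step 4: are unequal removals needed?** No. Remove 3 of 20 in each arm, with zero week-16 change in all six. The all-randomised difference is 3.3 × 0.85 − 0.06 × 0.85 = 2.805 − 0.051 = 2.754, and 3.24/2.754 is again 1.18.

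**Step 5: is the sign fixed?** No. If the three show no change at an early exit visit but would have reached half the effect by week 16, the plan estimates 2.745 where the all-randomised value is 2.99: 2.745/2.9925 = 0.92, an understatement of 8%. If removed diet-arm subjects would have gained fat, losing them also makes the exercise advantage look smaller.

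**Step 6: consequence for power.** With all 40 followed and a difference of 2.75, at the planning SDs, power is 99% in the most favourable scenario of Step 1 and 67% in the least favourable.

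**The case against.** The plan is not careless about withdrawn subjects. Section 12.2 asks them to repeat all baseline assessments, bars replacement and commits to intent-to-treat. The right to decline procedures belongs to the subject, and no rewording removes it. Section 7 lets the investigator extend or restart an interrupted intervention and allows self-paced accommodation, which may narrow what counts as non-compliance. A midpoint DXA is scheduled, so subjects who leave late may have an intermediate %BF value.

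Much of this stands as mitigation. It does not remove the conflict. The interruption clause covers illness and personal reasons and does not override the removal rule. The midpoint scan helps %BF only; insulin sensitivity, glucose effectiveness, BMR, CT fat volumes and epicardial fat have no such value. Nothing says how an early or absent outcome enters the analysis.

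A reader might infer four stronger claims that the documents do not support:

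- **That the rule acts on the exercise arm only.** It covers both arms, and both have weekday app contact and a weekly teleconference. The exercise arm adds 200 minutes a week of cycling, so more removals there are plausible, but no arm-specific rate is given.
- **That subjects are assessed on leaving.** This is the likely reading, given the bar on later follow-up, but Section 12.2 gives no date.
- **That intent-to-treat is defeated.** Exit data are requested, so a randomised-set analysis remains possible, at unequal and unstated times.
- **That 18% or more is the expected bias.** The 18% needs no exit data and no benefit in every removed subject. Applying the 80% completion in Section 3.2 (4 of 20 lost: 3.3 × 16/20 − 0.06 = 2.58; 3.24/2.58 = 1.26) would give 26%, but that figure comes from 17 veterans with paraplegia in an equipment pilot, a different population and setting.

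**Conclusion.** The point holds in this form: Sections 12.1 and 12.2 do not separate stopping the intervention from leaving the study, and so undermine the intent-to-treat analysis stated in Sections 7 and 12.2. This applies to both arms. The size and direction of the bias cannot be fixed from the documents.

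On the planning values, with 3 of 20 exercise subjects removed and no week-16 exercise benefit in them, the %BF difference is overstated by 0% to 18% depending on whether exit data are obtained and what they show. The number removed and the absence of benefit are assumptions; under others the sign can reverse. It should be corrected because it bears on the primary comparison and costs little.

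**What to change.** 1. **Section 12.1:** state that non-compliance does not end study participation for outcome assessment, and define what counts as non-compliance.
2. **Section 12.2:** state that every randomised subject who has not withdrawn consent is invited to the End of Study assessment at its scheduled Week 21 time. Say how that week is counted when the intervention was extended or restarted. Section 20.5 refers to a Week 22 visit and should be reconciled.
3. **Section 10:** analyse the Week 21 value in the randomised arm. Keep any early-exit value as an additional repeated measure only. Pre-specify how missing final values are handled, with a sensitivity analysis that does not assume removed subjects resemble those who stayed.
4. **Reporting:** give removals by arm and reason, and the timing of every exit assessment.

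The assessment is already planned for all subjects, so the cost is protocol wording plus modest effort to bring back non-adherers. Subjects may still decline. Including them may also lower power if they truly benefit less (Step 6); that is the price of estimating the stated effect.

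The stated enrolment windows (to December 2024 in the Study Timelines, to December 2022 in Section 21) precede this version's date stamp (071825). If enrolment and follow-up have ended, items 1 and 2 will reach few or no subjects, but the sensitivity analysis and the reporting in items 3 and 4 remain feasible.
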